7.2.6 Incidence of recurrent venous thromboembolism within 90 days of diagnosis

The number of patients who were indicated for warfarin therapy due to venous thromboembolism (VTE) who experienced recurrence within 90 days of diagnosis will be tabulated for each study group. The risk ratio will be used to compare the effect size between study groups, and the P-value will be calculated using the Chi-square test.

7.2.7 Percentage of time spent within therapeutic INR range

The Percentage of Time in Therapeutic Range (PTTR) will be calculated using a linear interpolation method as described by Rosendaal et al (1993) [4]. If the INR value is unavailable at baseline, it will be assumed to be 1.0. The PTTR will be calculated only for patients who received at least 12 days of treatment. Comparison between groups will be performed using a t-test, with data transformations as required.

The endpoint of "Percentage of Time in Therapeutic Range (PTTR)" was introduced by recommendation of the Scientific Review Committee for the **S**urveillance **A**nd **Ph**armacogenomics Initiative for Adverse Drug **RE**actions (SAPhIRE) programme. It was deemed that reporting of this endpoint would facilitate between-trial comparisons with previous studies, and enable meta-analyses of trials evaluating the utility of pharmacogenetics-guided dosing of warfarin.

7.2.8 Accuracy and precision of the pharmacogenetic maintenance doseprediction model

This endpoint seeks to compare the predicted warfarin maintenance dose vs actual maintenance dose for patients in the pharmacogenetics arm who have achieved stable dose. The accuracy and precision of the model will be evaluated using the mean percentage error (MPE%) and root mean squared error (RMSE%) respectively.

Protocol Version and Date: Version 13, April 2014 SAP Version and Date: Version 1, June 2016

7. References

- Tham L-S, Goh B-C, Nafziger A et al. A warfarin-dosing model in Asians that uses single-nucleotide polymorphisms in vitamin K epoxide reductase complex and cytochrome P450 2C9. Clin. Pharmacol. Ther. 2006; 80(4):346–55.

Protocol No: PG01/11/06

A Randomized Controlled Trial to Assess the Clinical Benefits of a Pharmacogenetics-Guided Dosing Regimen for Calculating Warfarin Maintenance Dose

Principal Investigator:	[name] [name] ¹
	[contact]
	[contact]
	Email: [contact]

Co-Investigators:

National University Hospital and National University of Singapore:

[name] [name]¹ [name] [name] [name] [name]¹ [name] [name]¹ [name] [name] [name]³ [name] [name] [name]⁴ [name]⁵ [name] [name]⁷

[name] [name]⁸ [name]

Tan Tock Seng Hospital:

[name] [name]⁹ [name] [name]⁹ [name] [name] [name]¹¹

University of Malaya Medical Centre:

[name] [name]¹² [name] [name] [name]¹² [name] [name] [name]¹²

¹: Department of Haematology-Oncology, National University Health System, Singapore

Protocol No: PG01/11/06 Version 13, 24 April 2014 ²: Department of Surgery, National University Health System, Singapore

³: Department of Medicine, National University Health System, Singapore

⁴: Dept of Cardiology, National University Health System. Singapore

⁵: Department of Pharmacy, National University Health System. Singapore

⁶: Oncology Research Institute, National University of Singapore

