2.1 Changes to Study Protocol

The SAP summarises the statistical design and methodologies presented in the April 2014 version of the study protocol; and where differences exist, supersedes the study protocol. Any changes to the study protocol as listed in this SAP have been submitted to and approved by the Domain Specific Review Board (DSRB) of the National Healthcare Group (NHG). Any differences with the study protocol are clearly described, and the rationale for the amendments explained.

3. Study Objectives

The primary objective is to assess the clinical benefits of genotype-guided dosing of warfarin against the traditional mode of dosing which uses only clinical factors.

The secondary objective is to prospectively evaluate the accuracy and precision of the pharmacogenetic dose-prediction model used to calculate the maintenance dose for patients in the pharmacogenetics arm [1].

4. Study Design

This is a multicentre, open-label, randomised controlled trial which uses a noninferiority study design. Patients newly indicated for warfarin therapy will be randomised 1:1 to receive pharmacogenetics-guided or the traditional dosing regimen. The therapeutic International Normalised Ratio (INR) range is considered to be >1.9 and \leq 3.1.

The disposition of patients who were screened for eligibility will be summarised in a CONSORT flow diagram [2].

Protocol Version and Date: Version 13, April 2014 SAP Version and Date: Version 1, June 2016

5. Sample Size Calculation

The sample size of 270 (135 in each study arm) provides 80% power to detect a non-inferiority margin of 0.5 with a one-sided alpha of 0.05, given a betweengroup difference in mean number of dose titrations of 1.0 and common standard deviation of 1.4. Primary analysis will use the intention-to-treat population, which will include patients evaluable for the primary endpoint at 12–14 days

Assuming an attrition rate of 15% after randomisation, approximately 320 patients would be enrolled and randomly allocated in a 1:1 fashion to the study groups.

6. Reporting of Patients Baseline Characteristics

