Appendix 1A16	
Appendix 1B 16	
Appendix 2B 16	
Appendix 3	
Appendix 4	

A Randomized Controlled Trial to Assess the Clinical Benefits of a Pharmacogenetics-Guided Dosing Regimen for Calculating Warfarin Maintenance Dose

Synopsis

Background: Interethnic differences in warfarin dose requirements in the Asian population have been well described. Our previous studies showed that warfarin maintenance doses in our multi-ethnic population were closely related to patient demographics and genetic polymorphisms in cytochrome(CYP)P4502C9 and vitamin K epoxide reductase complex subunit 1(VKORC1). A retrospective regression model combining these predictors accounts for 57.8% of the variability in warfarin dose.

Hypothesis: We hypothesize that warfarin dose requirement could be more accurately predicted using a simplified genotyping procedure requiring the identification of a single CYP2C9 allele and a single nucleotide polymorphism of VKORC1 to discern between the 2 major haplotypes H1 and H7.

Aims: The aim is to compare the clinical benefits of genetics-guided dosing versus traditional trial and error dosing with protocol guided-adjustments. Two secondary objectives are (1) to prospectively evaluate a dosing algorithm built on demographics and genetic predictors; (2) to assess the feasibility of a simplified test for CYP2C9*3 and VKORC1 SNP in clinical practice.

Methodology and Statistical Analysis: Details of the statistical design and methodologies for this trial are summarized in the Statistical Analysis Plan (SAP).

Significance: This concerted, multi-disciplinary effort to bring pharmacogenetics-based therapy from bench to bedside has the potential to reduce the efforts incurred with multiple dose titrations of the most commonly prescribed oral anticoagulant. With the aid of mathematical modeling, a simplified and more cost-effective genotyping method could be implementation for the future treatment and prophylaxis of thromboembolic diseases.

1. Background

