2.2 Hypothesis and study objectives

We hypothesize that warfarin dose requirement could be more accurately predicted using a simplified genotyping procedure requiring the identification of a single CYP2C9 allele and a single nucleotide polymorphism of VKORC1.

The primary objective is to assess the clinical benefits of genotype-guided dosing of warfarin against the traditional mode of dosing which uses only clinical factors.

The secondary objective is to prospectively evaluate the accuracy and precision of the pharmacogenetic dose-prediction model used to calculate the maintenance dose for patients in the pharmacogenetics arm.

3. Patient Selection

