4.5 Warfarin Administration

All predicted warfarin dose will be administered by rounding down to the nearest 0.5 mg. Warfarin (Marevan®) is available as 1mg (brown), 3 mg (blue) and 5 mg (pink) oral tablets from GlaxoSmithKline Pte. Ltd. Patients and/or their caregivers will be given dietary advice upon initiation of warfarin therapy to avoid drug-food interactions affecting warfarin pharmacokinetics.

Suitable alternatives of warfarin or generic drugs may be used instead.

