Appendix 2B

INR	Actions	
<1.5	Increase warfarin dose by 25% (round down to nearest 0.5mg).	
	Re-check INR the next day	
1.51-3	Maintain same warfarin dose	
3.01-3.5	Reduce warfarin dose by 25% (round down to nearest 0.5mg)	
3.51-4	Reduce warfarin dose by 50% (round down to the nearest 0.5mg)	
	Re-check INR the next day	
>4	Omit dose for the day. Re-check INR the next day	

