Appendix 3.

Warfarin Dosing Algorithm for ACC Harmonised Clinic during maintenance phase

If INR < 2 or >3, venous INR should be obtained as the correct INR value

INR	ACTION		
< 1.5	Increase dosage by 1mg / dose; repeat blood test for INR in 7 days NB. If patient has prosthetic heart valve, inform doctor-in-charge immediately*		
1.5-1.9	Increase dosage by 0.5mg / dose; repeat blood test for INR in 7 - 10 days		
2.0-3.0	No change		
3.1-3.4	 No bleeding : Repeat INR within 2 weeks if INR is in range on same dose previously for more than 6 months and patient does not have obvious bleeding risks, otherwise: Decrease dose by 0.5mg 		
3.5-4.0	No bleeding: decrease dosage by 0.5mg / dose; repeat blood test for INR in 7 days		
4.1-5.0	Bleeding: inform doctor-in-charge of patient immediately* No bleeding: stop warfarin for 2 days; decrease dosage by 1mg / dose; repeat blood test for INR in 5 - 7 days Bleeding: inform doctor-in-charge of patient immediately*		
5.1-5.5	No bleeding: stop warfarin for 3 days; repeat blood test for INR in 3-5 days; restart warfarin if INR is in therapeutic range (decrease dosage by 1.5mg); Bleeding: inform doctor-in-charge immediately*		
> 5.5	Stop warfarin; inform doctor-in-charge immediately*		

Guideline for Follow-up Visits

INR	Variation	Assessment Date
Out of range	-	3-10 days
(refer to Appendix 3-		
Warfarin Dosing		
Algorithm)		
Within target range	≥ 0.8 units	4-6 weeks
	< 0.8 units	3 months

NB. A repeat blood test should be performed 1 week to 10 days later for all NEW patients (i.e. first-timers) to check the INR so that the dose may be confirmed, even if the initial INR after discharge is within target range.

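### SAP 7.2.8 scores the dose model only in the arm that started on its doses and against no genotype-free reference, although control genotypes are already planned

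*SAP*

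**What the plan says.** The only planned analysis of dose prediction is SAP 7.2.8, which aims to "compare the predicted warfarin maintenance dose vs actual maintenance dose for patients in the pharmacogenetics arm who have achieved stable dose". Accuracy is MPE% and precision is RMSE%, for one model. The section names no reference predictor and no confidence interval, and does not use the control arm.

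The secondary objective (SAP section 3, repeated in protocol 2.2) is to "evaluate the accuracy and precision of the pharmacogenetic dose-prediction model used to calculate the maintenance dose for patients in the pharmacogenetics arm". Protocol 2.2 also states a comparative hypothesis: "warfarin dose requirement could be more accurately predicted using a simplified genotyping procedure". It does not name the comparator.

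On dosing in the pharmacogenetics arm:
- Protocol 4.5: "All predicted warfarin dose will be administered by rounding down to the nearest 0.5 mg".
- Protocol 4.2: the tailored dose is the starting dose if genotype results are available; otherwise the patient moves to the standard scheme by day 5.
- Appendices 2A and 2B, at INR 1.51-3: "Maintain same warfarin dose".
- Appendix 3 (maintenance phase), at INR 1.5-1.9: "Increase dosage by 0.5mg / dose; repeat blood test for INR in 7 - 10 days".

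Control patients start on fixed doses. After the first INR, Appendix 1A gives them 4, 3 or 2 mg, or omits the dose above INR 3.5. Protocol 4.1 stores their blood for genotyping at the end of the study. No SAP analysis uses those genotypes.

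**The concern.** A range of doses can hold one patient's INR in range. Where a patient settles within that range depends partly on where dosing started. In the pharmacogenetics arm it starts at the model's prediction, so predicted and actual dose are not independent, and agreement can look better than it would for a patient dosed without the model.

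A single-model error also has no yardstick. MPE% and RMSE% for the full model do not show how much of the accuracy comes from genotype and how much from age and weight, or whether a fixed dose would do nearly as well. That increment matters for a trial whose rationale (protocol 2.1) is that simplified genotyping could be cost-effective in routine practice. The data for a better estimate are already planned and would go unused.

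**Working it through.** **1. What each planned analysis measures.** SAP 7.1 and 7.2.1 to 7.2.7 compare the arms on titrations, time to stable INR, dose adjustments, INR checks, INR above 3.0, bleeding, recurrent VTE and time in range. None measures prediction error. SAP 7.2.8 does, for one model in one arm.

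**2. The model's error before the trial (protocol 4.4).** In the 109 validation patients the under-prediction was 0.37 ± 1.26 mg/day. Reading 1.26 as an SD, RMSE = √(0.37² + 1.26²) = √(0.1369 + 1.5876) = 1.31 mg/day.

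**3. A pharmacogenetics patient whose dose is never changed.** The only error is rounding, between 0 and just under 0.5 mg. A prediction of 3.4 mg given as 3.0 gives (3.4 − 3.0)/3.0 = 13.3%; 2.4 given as 2.0 gives (2.4 − 2.0)/2.0 = 20%. In mg, this is well below the 1.31 mg/day of step 2.

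**4. Possible size across the arm, by simulation.** Inputs from the documents: R² = 0.592, SD of predicted minus actual dose 1.26 mg/day, and rounding down to 0.5 mg. Assumptions not in the documents:
- Lognormal requirement, median 3.0, 3.5 or 4.0 mg/day, with log SD 0.519, 0.466 or 0.423 chosen to give the 1.26.
- Results always arrive in time.
- The dose is kept if within 10, 20 or 30% of the requirement, and otherwise moved in 0.5 mg steps until it is.
- Controls start at 3 mg.

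Full-model RMSE%, with relative fall = 1 − (pharmacogenetics arm ÷ unanchored):

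| Median, tolerance | Against true requirement | Pharmacogenetics arm | Relative change |
|---|---|---|---|
| 3.0 mg, 10% | 36.1 (another run 36.5) | 35.8 (37.2) | fall of 1% (rise of 2%) |
| 3.5 mg, 20% | 32.3 | 26.2 | fall of 19% |
| 4.0 mg, 30% | 28.7 | 16.3 | fall of 43% |

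At 10% tolerance the change across the medians runs from a slight rise to about a 4% fall. In the 3.5 mg, 20% cell the control RMSE% is 31.9 to 32.2 across runs, against 32.3 unanchored. At 20-30% tolerance the control value stays at or somewhat above the unanchored value in most cells.

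**5. How precise a genotype-free comparison could be.** Assume 68, 101 or 135 controls with a stable dose and a full-model R² of 0.592. The chance that a paired 95% CI excludes no gain is:
- about 90, 98 and over 99% if the clinical-only R² is 0.30;
- about 45, 63 and 76% if it is 0.50;
- with controls anchored at 3 mg (median 3.5 mg, 20% tolerance), 58, 76 and 87% at R² 0.30, and 22, 34 and 44% at 0.50.

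The documents give no clinical-only R².

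**The case against.** The strongest reply is that 7.2.8 delivers its stated secondary objective, so nothing is contradicted. That stands as far as it goes. But the objective does not require the restriction: its reference to the pharmacogenetics arm describes what the model is used for, not where it must be scored.

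A reader might infer that the reported error is certain to be flattering. The documents do not support that. The tolerance is assumed, at 10% there is little or no effect, and rounding down, Appendix 3 changes and late genotype results all loosen the link. A kept dose with a stable INR is also partly genuine predictive success.

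A reader might also infer that the protocol hypothesis goes untested. That is too strong, because its comparator is unnamed. Nearby text contrasts genotype guidance with dosing that ignores genetics and with "traditional trial and error dosing with protocol guided-adjustments", and simplified with more detailed genotyping. What can be said is that no planned analysis compares prediction with and without genotype. The randomised comparison does not supply one: it sets "genotype-guided dosing of warfarin against the traditional mode of dosing which uses only clinical factors", a valid contrast of whole regimens, but these also differ in use of weight, starting scheme and first-INR rule.

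Nor are control doses free of any anchor. They are pulled towards the 4, 3 or 2 mg steps of Appendix 1A, and the simulation's 3 mg start with 0.5 mg steps is only a rough stand-in for those steps and for the 25% and 50% changes in Appendix 1B. Those steps do not, however, come from the model being scored.

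**Conclusion.** The point holds as a worthwhile improvement, not as an error that undermines the trial. Two parts rest on the documents alone: the model is scored only where its own prediction set the starting dose, and there is no reference predictor. That the error may be understated follows from the dosing rules. Its size, from about none at 10% tolerance to about 40% at 30%, rests wholly on the assumptions listed. Scoring the model in controls gives an estimate not anchored to the model, though not a bias-free one. The primary test, the other endpoints and the validity of the regimen comparison are unaffected.

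**What to change.** Amend SAP 7.2.8 before the control genotypes are analysed:

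1. Apply the model also to control patients with a stable dose, using the planned retrospective genotypes. Report MPE% and RMSE% by arm with 95% CIs.
2. State that pharmacogenetics-arm doses are anchored to the prediction. Treat the control result as the estimate not anchored to the model, noting that control doses start from the Appendix 1A steps.
3. As exploratory, report a genotype-free reference in the same patients, with the paired error difference and 95% CI. This can be a fixed dose, or an age-plus-weight model fitted in the original 111-patient building data if they are available. If they are not, cross-validate both predictor sets in controls.

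This needs no new patients, samples or visits: control genotyping is planned, and age and weight are collected from everyone (protocol 4.3). It costs a short addition to the text, a table and a modest amount of analysis.

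Downsides: the control table waits for end-of-study genotyping, and the reported accuracy may look less favourable. Precision is limited. The 135 per arm in SAP section 5 are patients evaluable at days 12-14, and the number with a stable dose may be well below that, above all if the protocol 4.2 definition applies (no dose change for at least 3 months, in a follow-up of about 3 months).

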Appendix 1A16	
Appendix 1B 16	
Appendix 2B 16	
Appendix 3	
Appendix 4	

A Randomized Controlled Trial to Assess the Clinical Benefits of a Pharmacogenetics-Guided Dosing Regimen for Calculating Warfarin Maintenance Dose

Synopsis

Background: Interethnic differences in warfarin dose requirements in the Asian population have been well described. Our previous studies showed that warfarin maintenance doses in our multi-ethnic population were closely related to patient demographics and genetic polymorphisms in cytochrome(CYP)P4502C9 and vitamin K epoxide reductase complex subunit 1(VKORC1). A retrospective regression model combining these predictors accounts for 57.8% of the variability in warfarin dose.

Hypothesis: We hypothesize that warfarin dose requirement could be more accurately predicted using a simplified genotyping procedure requiring the identification of a single CYP2C9 allele and a single nucleotide polymorphism of VKORC1 to discern between the 2 major haplotypes H1 and H7.

Aims: The aim is to compare the clinical benefits of genetics-guided dosing versus traditional trial and error dosing with protocol guided-adjustments. Two secondary objectives are (1) to prospectively evaluate a dosing algorithm built on demographics and genetic predictors; (2) to assess the feasibility of a simplified test for CYP2C9*3 and VKORC1 SNP in clinical practice.

Methodology and Statistical Analysis: Details of the statistical design and methodologies for this trial are summarized in the Statistical Analysis Plan (SAP).

Significance: This concerted, multi-disciplinary effort to bring pharmacogenetics-based therapy from bench to bedside has the potential to reduce the efforts incurred with multiple dose titrations of the most commonly prescribed oral anticoagulant. With the aid of mathematical modeling, a simplified and more cost-effective genotyping method could be implementation for the future treatment and prophylaxis of thromboembolic diseases.

1. Background

To date, warfarin remained the most widely prescribed oral anticoagulation agent for long-term prophylaxis and treatment of thromboembolic disorders^{1,2}. Since warfarin has a narrow therapeutic index, the discovery of the close association of its dose requirements with genetics polymorphisms in recent years has re-ignited much interest. This drug that has been available since the 1950s is an ideal candidate model for testing the paradigm of pharmacogenetics-based dosing.³ Previous pharmacogenetics studies showed cytochrome P450 (CYP) 2C9 genotypes to be closely associated with warfarin dose requirements as it undergoes metabolism by this polymorphic enzyme ⁴⁻¹¹ The common CYP2C9*1 is considered the wild-type allele while single nucleotide polymorphisms (SNPs) at exon 3, 430C>T for CYP2C9*2 and exon 7, 1075 A>C for CYP2C9*3 are the more common mutants. A recent review by Voora et al summarized the allele frequency of CYP2C9 by ethnic groups.¹² The CYP2C9*1 allele was present in about 80% of the Caucasian population, CYP2C9*2 and CYP2C9*3 accounted for 13% and 7% respectively of the remaining population. The genetic distribution in the Asian population showed predominance of the wild type, a slightly higher distribution of CYP2C9*3 at 18% while CYP2C9*2 was rarely seen. Our previous study showed that CYP2C9*3 was identified in all 3 Asian ethnic groups in Singapore but CYP2C9*2 was not detected in this study comprising 125 patients.⁸ Warfarin maintenance was higher for Indians compared to Chinese and Malays. The lowest occurrence of CYP2C9*3 was in Chinese (7%), followed by Malays (11%), then Indians (15%). However, the genetic variants of CYP2C9 alone were insufficient to explain for the difference in maintenance dose requirements between the ethnic groups. More recent findings showed that vitamin K epoxide reductase complex subunit 1 (VKORC1) had a larger impact than CYP2C9 on warfarin dose. This greatly enhanced the predictability of warfarin dose requirements.¹³⁻¹⁵ This was confirmed in our local population. VKORC1 variants when assigned to haplotypes based on the method described by Reider, successfully accounted for the difference in warfarin requirements between the Asian ethnic groups that CYP2C9 alone was unable to predict accurately.^{13,22} The H1 and H7 haplotypes alone accounted for more than 95% of the haployptes in Chinese and Malays while Indians showed slightly more diversity, with 4 haplotypes (H1, H7, H8 and H9) accounting for 93% of all haplotypes. Therefore, despite the multi-ethnicity, the lack of genetic diversity in the local population allowed VKORC1 genotyping with just one single-nucleotide polymorphism (SNP), at position 381 of the reference sequence (GenBank accession number AY587020), to be sufficient to discern the 2 major haplotypes (H1 and H7). Since the CYP2C9*2 variant was rare in our population, being present in 0%, 1% and 4% in Chinese, Malays and Indians respectively, and the CYP2C9*3 variant was more common being present in 7%, 9% and 8% for Chinese, Malays and Indians respectively, it was safe to "misclassify" the intermediate-metabolizers with the CYP2C9*2 variant with the slow-metabolizers bearing the CYP2C9*3 allele, introducing a deliberate bias toward under-prediction and creating a binary variable for the CYP2C9 predictor.¹⁶

While it is obvious that demographic, environmental and genetic factors all contribute to the vast inter-individual variability in warfarin dose requirements, traditional dosing algorithms used in guiding its prescribing did not account for the known genetic influence.¹⁷⁻²² It was in 2005 that the only prospective study validating the clinical utility

of a retrospectively developed pharmacogenetics-guided dosing algorithm using CYP2C9 genotype-guided dosing of warfarin in elective surgical patients showed potential feasibility. It predicted 42% of the variance in maintenance warfarin dose.^{19, 23} A study incorporating both CYP2C9 and VKORC1-1639 genotypes further enhanced this application of pharmacogenetics-guided dosing by increasing the accountability of variability in dose to 54.2% and underpredicts daily maintenance requirements in a small validation sample dataset (n = 38) by 0.2 ± 0.8 mg/day.²⁴ Our current model compares favorably with this in terms of accounting for variability in dose (R² = 0.592), despite using a much less detailed genotyping procedure due to the unique genotypic distribution in our population. This offers a great opportunity to bring pharmacogenetics-guided dosing from bench to bedside.

2. Rationale and Hypothesis

